9.2 Analyses

All analyses are ITT, unless specified otherwise. Evaluable subjects will be individuals who agree to participate in the vitamin D substudy. The primary endpoint analysis will use a paired t-test to compare the changes in P1NP levels from week 24 to 48 weeks between cases and matched controls. Secondary endpoint analyses will include comparison of changes in 25-OH vitamin D levels, PTH, and CTX and will be analyzed analogously to the primary endpoint. If parametric assumptions fail, the corresponding non-parametric test will be applied, in this case, the Wilcoxon signed rank test. Sensitivity analyses will include linear regression models that adjust for possible confounding covariates, such as dietary intake.

Matching: Concurrent controls who are not enrolled in the vitamin D substudy who are reporting supplementation with ≤ 400 IU of vitamin D/day will be matched 1:1 by randomization arm in the CCTG 595 main study (text messaging arm vs. standard of care), age (± 5 years), race/ethnicity, season of study entry, and BMI (± 3 kg/m²).

REFERENCES

1. DHHS Panel on Antiretroviral Guidelines for Adults and Adolescents. Guidelines for the use of antiretroviral agents in HIV-1-infected adults and adolescents. 2014; <http://www.aidsinfo.nih.gov/ContentFiles/AdultandAdolescentGL.pdf>. Accessed May 1, 2014.

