6.4 Schedule of Evaluations for Subjects On-Study, Off-Medications

6.4.1 At any point, subjects may elect to stop study medications but remain on study. Subjects that stay on study but stop medications will not be allowed to resume again.

Subjects will follow the same schedule as defined in Section 6.1 until the end of study. Study medications will not be dispensed at clinic visits, and evaluations related to counseling or monitoring of medications (including urine dipstick and serum creatinine) will not be performed. These include Adherence and Risk-reduction counseling and collection of dried blood spots. If the subject was randomized to the iTab arm, their account will be switched to “inactive.”

STI and HIV rapid test screenings and questionnaires will still be administered as the schedule dictates.

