3.0 STUDY DESIGN

CCTG 595 is an open-label clinical trial of the effect of a text messaging intervention vs. standard of care on adherence to Truvada as PrEP in MSM at increased risk for HIV infection (ClinicalTrials.gov Identifier: NCT01761643). Eligible subjects for this matched case control substudy will receive vitamin D 4000 IU/day for 24 weeks, from week 24 through week 48. In CCTG 595, plasma from participants are being collected and stored at entry and every 12 weeks. These plasma samples will be used to measure P1NP, CTX, PTH, and vitamin D levels in both cases and controls at entry, week 24, and week 48.

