4.0 SELECTION AND ENROLLMENT OF SUBJECTS

4.1 *Inclusion Criteria*

4.1.1 All subjects must meet CCTG 595 inclusion criteria.

4.2 *Exclusion Criteria*

4.2.1 All subjects must meet CCTG 595 exclusion criteria.

4.2.2 Current or prior use of bisphosphonate therapy.

4.2.3 Current use of vitamin D supplements greater than 400 IU/day.

4.2.4 Current use of androgenic hormones or growth hormones.

4.2.5 History of nephrolithiasis (kidney stones).

4.2.6 History of fragility fracture.

4.2.7 No use of tenofovir prior to entry into CCTG 595

4.3 *Study Enrollment Procedures*

Once a candidate for study entry has been identified, details will be carefully discussed with the subject. The subject will be asked to read and sign the approved protocol consent form. Participation in this substudy is not required for continued participation in CCTG 595.

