8.0 CRITERIA FOR DISCONTINUATION

8.1 Permanent Treatment Discontinuation

- Drug-related toxicity
- Requirement for prohibited concomitant medications
- Subject develops a kidney stone (see section 7.3.1).
- Completion of treatment as defined in the protocol.
- Request by subject to discontinue treatment.
- Discontinuation of PrEP for any reason
- Clinical reasons believed serious by the physician, even if not addressed in the toxicity section of the protocol.

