9.0 STATISTICAL CONSIDERATIONS

9.1 Sample size justification

In ACTG 5280, administration of vitamin D-calcium resulted in a significant reduction in

the magnitude of the rise in BTMs P1NP and CTX ⁹. Because of more consistent association with changes in BMD with P1NP, this will be used as the primary surrogate marker to reflect bone health. Data on TDF effects on P1NP levels in the absence of HIV infection (e.g. during PrEP) are not available. In A5280, at week 24 P1NP increased by 60% with placebo and 36% with vitamin D-calcium ($p < 0.001$). If we anticipate that supplementation with vitamin D results in a decrease of similar magnitude from week 24 to week 48, then the expected intervention effect size is in the range of 24%. The SD of the change in P1NP at month 6 for the vitamin D-calcium group was 63%, but it is anticipated that the variability of P1NP levels in this study will be much less than that in HIV infected subjects undergoing a variety of pro- and anti-inflammatory changes after initiation of ART as in A5280. If we anticipate that in the absence of vitamin D supplementation that P1NP will increase by 20% and those receiving vitamin D will experience a reduction of this amount at week 48, then with an SD of the change in P1NP of 40%, a sample size of 44 cases and 44 controls will provide 80% power to detect a significant difference in the change in P1NP from week 24 to week 48 between cases and controls using a paired t-test with a two-sided $\alpha = 0.05$. In order to account for attrition, a sample size of 100 is proposed, consisting of 50 vitamin D treated cases and 50 matched controls.

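### Vitamin D sub-study: controls need not be on TDF/FTC at week 24, although cases start vitamin D while on PrEP, so off-PrEP controls can shrink the P1NP difference toward no effect

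*Combined protocol and SAP*

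**What the plan says.** **Cases.** Sub-study section 3.0 states: "Eligible subjects for this matched case control substudy will receive vitamin D 4000 IU/day for 24 weeks, from week 24 through week 48". The regimen row of the sub-study schema places those weeks within PrEP with Truvada. Sub-study section 8.1 lists "Discontinuation of PrEP for any reason" as a reason to stop vitamin D permanently. Section 4.2 sets exclusions, among them "Current or prior use of bisphosphonate therapy", vitamin D supplements above 400 IU/day, androgenic or growth hormones, kidney stones, fragility fracture and earlier tenofovir use.

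**Controls.** Sub-study section 9.2 gives a separate rule: "Concurrent controls who are not enrolled in the vitamin D substudy who are reporting supplementation with ≤ 400 IU of vitamin D/day will be matched". Each case gets one control, and five factors define the match (main-study arm, age, race/ethnicity, season of study entry, BMI). PrEP status is neither a requirement nor a matching factor. Of the section 4.2 exclusions, only the 400 IU/day limit is repeated.

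**Subjects off PrEP.** Main protocol section 6.4 lets subjects stop study medication and remain on study: "Subjects will follow the same schedule as defined in Section 6.1 until the end of study". Those who choose to stop may not resume. Main protocol section 6.3.11 has plasma stored at all visits, and the sub-study measures P1NP on that stored plasma.

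**Size.** Sub-study section 9.1 states that "a sample size of 44 cases and 44 controls will provide 80% power", using a two-sided paired t-test at 0.05. It assumes a 20% rise in P1NP without vitamin D, removal of that rise with it, and an SD of the change of 40%.

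**The concern.** The sub-study hypothesis is that vitamin D blunts the rise in bone turnover markers that follows the start of TDF/FTC. The contrast is therefore informative only if the unsupplemented group is exposed to the drug. A case is on PrEP when vitamin D starts; a control may have been off it for weeks or months. A control who chose to stop before week 24 cannot restart under section 6.4, so he is unexposed for the whole measurement window.

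None of the five matching factors captures PrEP status. The intention-to-treat principle treats stopping after week 24 alike in both groups, but does nothing about unequal conditions at week 24. At stake is a false negative: a real vitamin D effect could be diluted for a reason unrelated to vitamin D.

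**Working it through.** **1. Can an off-PrEP subject meet the control rule?** Each condition in turn:

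- Not enrolled in the sub-study: yes.
- Reports at most 400 IU/day of vitamin D: possible.
- Matches a case on the five factors: possible, because none depends on PrEP use.
- Has week 24 and week 48 plasma: possible. Section 6.4 keeps the same schedule. The procedures it names as dropped are dispensing, urine dipstick, creatinine, adherence and risk-reduction counselling, and dried blood spots. Banked plasma is not named.

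Nothing in the sub-study schema or its sections 3.0, 4 and 9.2 requires a control to be on PrEP.

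**2. Reproducing the plan's 44 per group.** Section 9.1 gives two effect sizes (24% and 20%) and does not say whether the SD of 40% is per subject or for the pair difference.

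- Two-sample normal formula, difference 24, SD 40: n = 2 × (1.960 + 0.842)² × 40² / 24² = 43.6, so 44 per group. This reproduces the plan.
- Paired t-test, difference 20, SD of the pair difference 40: 34 pairs suffice, and 44 pairs give 90% power.
- Paired t-test, difference 20, 44 pairs, exactly 80% power: the SD of the pair difference must be 46.3. With a per-subject SD of 40 this means a within-pair correlation of 1 − 46.3²/(2 × 40²) = 0.33, which the plan does not state.

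Because the SD is ambiguous, both 46.3 and 40 are carried forward.

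**3. Dilution.** Let q be the share of controls off PrEP at week 24. The documents give no value; 10 to 20% is an assumption. Suppose their P1NP is flat, so each loses the planned 20-point rise.

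Diluted difference = 20 − 20q.

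Power comes from the noncentral t distribution with 43 degrees of freedom and noncentrality difference/(SD/√44). Here SD/√44 is 6.98 for SD 46.3 and 6.03 for SD 40.

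| q (assumed) | Difference | Power, SD 46.3 | Power, SD 40 |
|---|---|---|---|
| 0% | 20 | 80% | 90% |
| 10% | 18 | 71% | 83% |
| 20% | 16 | 61% | 74% |

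Mixing two kinds of control also adds q(1 − q) × 20² to the variance of the pair difference. At q = 20% that is 64, and power becomes 60% (SD 46.3) or 72% (SD 40).

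On the 24-point, two-sample base, with that variance included, q of 10 to 20% gives 22 to 20 points and power of 73 to 64%, from 80%.

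**The case against.** **Plasma may not exist for these subjects.** Section 6.4 drops evaluations that monitor medication, and names only STI tests, HIV rapid tests and questionnaires as continuing. Section 6.2.3 describes the plasma draw as being for FTC levels, and section 9.6.3 expects FTC results to be missing after discontinuation. On that reading an off-PrEP subject has no P1NP and cannot be a control. This stands as a doubt. But section 6.3.11 says plasma is stored at all visits and section 6.4 does not exempt it. A comparison should not rest on that ambiguity when one line of eligibility would settle it.

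**A reader might infer that users of bone-active drugs are also admitted as controls, again biasing toward no effect.** The documents do not support that as stated. The population row of the sub-study schema bars bisphosphonates, osteoporosis, fragility fracture, kidney stones and earlier tenofovir, without saying whether it covers controls. The direction is not shown either. The endpoint is a change, and stable bisphosphonate use may affect the level more than the change; androgenic or growth hormones could push a formation marker the other way. What stands is that the schema, section 4.2 and section 9.2 leave it unclear which exclusions bind controls.

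**The planned regression could adjust for PrEP status.** Its covariate list is open, but it is only a sensitivity analysis and names only dietary intake.

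**This is a pilot on a surrogate marker.** True, and the main trial's primary analysis is unaffected. That limits the importance of the point without removing it.

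**Conclusion.** The gap in the control rule is real for PrEP status: section 9.2, followed as written, can admit controls who are not exposed to TDF/FTC. For that route the bias runs toward no effect, given the plan's own premise of a 20% rise in unsupplemented subjects. Section 9.1 concedes that no data exist on P1NP under TDF without HIV infection, so the premise is itself an assumption.

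The size is illustrative. It rests on an assumed 10 to 20% of analysed controls being off PrEP, flat P1NP in them, plasma being available at both visits, and 44 complete pairs. On those terms 2 to 4 of the 20 points are lost, and power drops by 9 to 19 percentage points (SD 46.3) or 7 to 16 (SD 40). A larger loss would follow if P1NP fell after TDF/FTC was stopped, but the documents give no figure for such a fall. For the remaining section 4.2 exclusions, only the lack of clarity is established, not a direction of bias.

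**What to change.** In sub-study section 9.2:

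1. Require each control to be on TDF/FTC at the week 24 visit (drug dispensed, not in on-study, off-medication status), as the matched case is. Dispensing records and the discontinuation form already hold this.
2. Reconcile the schema population row, section 4.2 and section 9.2, so that the same section 4.2 exclusions apply to both groups as far as collected data allow. Medication history reaches back only 30 days before entry (main protocol section 6.3.3), so exclusions for prior use can be applied only in part; the text should say so.
3. Add a sensitivity analysis in pairs where both members have detectable FTC at week 24, using the plasma assay already planned. Any further restriction on week 48 FTC should be labelled supportive, because it is measured after vitamin D starts.

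The cost is wording and a filter on existing data, plus a smaller pool of matchable controls. The planned pool is 400 − 50 = 350 non-participants for 50 matches, before attrition and five-factor matching reduce it.

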Clinical Trials Specialist

[name]
Staff Research Associate
University of California, San Diego
Antiviral Research Center
[name]
San Diego, CA 92103
[contact]
[contact]
E-mail [contact]

Statistician

[name]
Associate Professor, Division of Biostatistics and Bioinformatics
Director, CCTG Biostatistics Core
Co-Director, Biostatistics Research Center (BRC)
University of California, San Diego
[name]
La Jolla, CA 92093-0717
[contact]
E-mail [contact]

Study Monitor and Data Unit

[name]
Medical Monitor, Study Coordinator, CCTG Data Unit
University of California, San Diego
Antiviral Research Center
[name]
San Diego, CA 92103
[contact]
[contact]
E-mail [contact]

Lab Technician

[name]
Phlebotomist and Lab Manager
University of California, San Diego
Antiviral Research Center

[name]
San Diego, CA 92103
[contact]
[contact]
E-mail [contact]

LIST OF ABBREVIATIONS

AE	Adverse Event
ALERT	Active Linkage, Engagement, and Retention to Treatment
ARV	Antiretroviral Therapy
CCTG	California Collaborative Treatment Group
CD4	CD4 Lymphocytes
CRF	Case Report Form
CT	Chlamydia
DSMB	Data Safety and Monitoring Board
GC	Gonorrhea
HAART	Highly Active Antiretroviral Therapy
HIV-1	Human Immunodeficiency Virus – 1
iTAB	Individualized Texting for Adherence Building
mITT	Modified Intention to Treat
MSM	Men who have Sex with Men
NAAT	Nucleic Acid Amplification Test
PLWH	Persons Living With HIV/AIDS
PrEP	Pre-Exposure Prophylaxis
RPR	Rapid Plasmin Reagin
SAP	Statistical Analysis Plan
SAE	Serious Adverse Event
SoC	Standard of Care
STI	Sexually Transmitted Infection
TPPA	Treponema Pallidum Particle Agglutination Assay
VAS	Visual Analog Scale
VDRL	Venereal Disease Research Laboratory

[figure not shown]
SCHEMA

Design: CCTG 595 is a controlled, open-label, two-arm, randomized (1:1) clinical demonstration project to determine if the use of a text-message based adherence intervention (iTAB) improves retention and adherence to PrEP compared to standard of care (SoC) PrEP delivery.

Duration: Each subject will be followed for up to 48 weeks after enrollment of the last subject to a maximum of 96 weeks. The primary endpoint will be measured at 48 weeks.

Sample Size: A total of 400 subjects will be randomized, 200 per arm.

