CCTG 595 Vitamin D Sub-study

Effect of Vitamin D Supplementation on Bone Turnover Markers during Tenofovir-Emtricitibine Pre-Exposure Prophylaxis in Men Who have Sex with Men

DESIGN	
CCTG 595 is an open-label clinical trial of the effect of text messaging intervention vs. standard of care on adherence to Truvada (tenofovir-emtricitibine) as PrEP in MSM at increased risk of HIV infection.
 
This sub-study is a matched case-control study, in which cases prospectively take vitamin D3 4000 IU/day beginning at week 24 of PrEP.

DURATION	
Subjects will be followed for 6 months (24 weeks)

SAMPLE SIZE	
50 eligible subjects will receive vitamin D and will be compared to 50 matched control subjects from CCTG 595 who are not participating in this sub-study.

POPULATION	
HIV-negative men aged ≥ 18 years initiating CCTG 595, who are not taking bisphosphonates and do not have a history of osteoporosis, fragility fracture, or kidney stones, or use of tenofovir prior to entry into CCTG 595

REGIMEN	
Vitamin D3 4000 IU/day from week 24 through 48 of PrEP with Truvada

ENDPOINTS	
Primary endpoint will be changes in bone turnover markers from week 24 through week 48 in the vitamin D intervention group as compared to age- and BMI-matched controls

ANALYSIS	
A sample size of 44 subjects per group will provide 80% power to detect a 20% change in P1NP means from week 24 through week 48 between matched cases and controls using a paired t-test with a two-sided $\alpha = 0.05$. To account for attrition, a sample size of 100 is proposed, including 50 vitamin D treated cases and 50 matched controls from CCTG 595.

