In ACTG 5280, vitamin D-calcium supplementation prevented the increase in parathyroid hormone (PTH) and blunted the increase in bone turnover markers (BTMs), including P1NP (a marker of bone formation) and CTX (a marker of bone resorption). Importantly, there was a good correlation between changes in DXA-measured BMD over time and changes in BTMs, particularly with P1NP. The percentage change of P1NP at week 48 correlated with the percentage change in total hip BMD ($r = -0.32$, $p = 0.01$) as well as the change in lumbar spine BMD ($r = -0.37$, $p = 0.002$) [Overton ET, unpublished data]. Due to the difficulties and expense of performing DXA scans in a clinical trial, P1NP levels are proposed as the primary outcome measure for this pilot trial.

CCTG 595 is an open-label clinical trial of the effect of a text messaging intervention vs. standard of care on adherence to Truvada as PrEP in MSM at increased risk for HIV infection (ClinicalTrials.gov Identifier: NCT01761643). Approximately 1/3 of the planned 400 subjects have been enrolled as of April 2014. Study sites include University of California at San Diego, University of Southern California, and Harbor-UCLA Medical Center.

Rationale for use of vitamin D dose: The dose of vitamin D (4000 IU/day) in this protocol carries little risk for the study subjects. This dose was without adverse effects in a more ill population, namely the HIV-infected subjects in ACTG 5280 (see above). Generally, vitamin D supplementation is well tolerated and safe. Dosages up to 10,000 IU daily in healthy adults is considered safe and the current upper U.S. Dietary Reference Intake of 2,000 IU daily is considered to be well below the actual physiologic requirements^{10,11}. The Institutes of Medicine guideline considers 4000 IU/day to be the safe upper limits for daily intake for adults <http://www.iom.edu/Reports/2010/dietary-reference-intakes-for-calcium-and-vitamin-D/DRI-values.aspx>. Several studies have focused specifically on the safety of chronic daily administration of 4000 IU¹²⁻¹⁴. In these studies, 228 adult subjects received 4000 IU/day vitamin D with excellent tolerability, no toxicity, and a concomitant increase in 25 (OH) vitamin D levels ranging from 39-51 ng/mL. No abnormalities in serum calcium or urinary calcium excretion were noted.

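### Vitamin D sub-study: the five-factor 1:1 matching rule is unlikely to yield all 50 pairs, the synopsis gives a different rule, and the sample size allows nothing for unmatched cases

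*Combined protocol and SAP*

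**What the plan says.** **Matching rule.** Sub-study section 9.2 (Analyses, Matching) draws controls as follows: "Concurrent controls who are not enrolled in the vitamin D substudy", taking no more than 400 IU of vitamin D a day. They "will be matched 1:1 by randomization arm in the CCTG 595 main study", and further on "age (± 5 years), race/ethnicity, season of study entry, and BMI (± 3 kg/m²". The primary analysis is a paired t-test on the change in P1NP from week 24 to week 48. Linear regression with covariate adjustment is planned as a sensitivity analysis.

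**Synopsis.** The Endpoints entry describes the comparison differently: "as compared to age- and BMI-matched controls". Arm, race/ethnicity and season are not mentioned.

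**Source of controls.** The main protocol's Schema states: "A total of 400 subjects will be randomized, 200 per arm". The sub-study synopsis says the 50 treated subjects "will be compared to 50 matched control subjects from CCTG 595 who are not participating in this sub-study".

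**Size.** Sub-study section 9.1 derives 44 cases and 44 controls for 80% power (20% difference, SD of the change 40%, two-sided 0.05, paired t-test). It then adds: "In order to account for attrition, a sample size of 100 is proposed, consisting of 50 vitamin D treated cases and 50 matched controls".

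**The concern.** Each extra exact-match factor divides the candidate controls for a given case. Five factors applied together leave few candidates per case, and a case with no candidate contributes nothing to a paired t-test. Section 9.1 treats attrition as the only route from 50 pairs to 44. The sub-study text contains no feasibility estimate, no rule for relaxing the matching and no rule for a pair with one missing value. It defines neither the race/ethnicity categories nor the seasons.

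At stake are the number of pairs behind the stated 80% power and the population to which the result applies, since the cases hardest to match are the ones dropped. The two statements of the matching rule also differ enough to change the answer on feasibility.

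**Working it through.** **1. The plan's own figure.** For a paired t-test the relevant SD is that of the within-pair difference, SD_d = SD × √(2(1 − ρ)), where ρ is the correlation of changes within a pair. Section 9.1 gives SD = 40% but no ρ. Power is from the noncentral t distribution for a 20% difference, two-sided 0.05.

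| Reading of the 40% | SD_d | Pairs for 80% | Power, 44 pairs | Power, 50 pairs |
|---|---|---|---|---|
| SD of the pair difference | 40 | 34 (81%) | 90% | not needed |
| Per-subject SD, ρ = 0 | 40 × √2 = 56.6 | 65 | 63% | 69% |

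Neither reading returns 44. That figure appears if SD_d is about 46.3, which means ρ = 1 − 46.3²/(2 × 40²) = 0.33 and is not stated. It also appears if the 24% effect mentioned in section 9.1 is put into an unpaired normal formula: 2 × (1.96 + 0.84)² × (40/24)² = 43.6, rounded up to 44.

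**2. The pool.** 400 − 50 = 350 potential controls at most. The concurrency and supplement restrictions reduce this by an unknown amount. When the sub-study was written, "Approximately 1/3 of the planned 400 subjects have been enrolled as of April 2014", which is about 133 subjects.

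**3. The allowance.** 44/50 = 0.88, so 12% of pairs may be lost for any reason. If controls are chosen among subjects with both samples, only cases can be lost, and the whole 12% is available for them. Nothing then remains for cases without a match.

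**4. Matching feasibility.** Fifty simulated cases were matched to a simulated pool by maximum 1:1 matching on all five factors, with two equal arms and equal seasons. All distributions are assumptions. The only related figure in the documents is the main protocol's target of at least 15% African American subjects (section 3.1). The race shares were 85/15, 60/25/15 or 50/25/15/10.

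| Setting (race groups, seasons, age SD / BMI SD) | Mean pairs, 350 controls | Mean pairs, 250 controls | P(50), 350 | P(≥44), 350 | P(≥44 complete) after 10% case loss, 350 |
|---|---|---|---|---|---|
| A: 2, 2, 6/3 | 48.3 | 47.5 | 0.18 | 1.00 | 0.53 |
| B: 2, 4, 7/3.5 | 45.0 | 43.1 | 0.01 | 0.77 | 0.14 |
| C: 3, 4, 7/3.5 | 42.1 | 39.0 | 0.00 | 0.29 | 0.03 |
| D: 4, 4, 9/4.5 | 35.2 | 30.9 | 0.00 | <0.01 | 0.00 |

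A wider grid (2 to 4 race groups, 2 or 4 seasons, age SD 6 to 10, BMI SD 2.5 to 4.5, 280 to 350 controls) gives averages of about 29 to 49 pairs. The chance of all 50 is at most about 0.26. Simulation error and the shape of the assumed distributions can move that by a few hundredths. With 10% of cases lost and no control loss, the chance of 44 complete pairs is below 0.5 in all but the two most favourable settings.

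**5. The synopsis rule.** Under setting D, matching on age and BMI only gives 49.5 pairs on average from 350 controls, with P(≥44) = 1.00 before attrition. The five-factor rule gives 35.2 in the same setting. The choice between the two texts therefore decides feasibility.

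**6. Power at fewer pairs.** At 35 pairs, power is 82% if SD_d = 40 and 53% if SD_d = 56.6. At 42 pairs the figures are 89% and 61%.

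**The case against.** Several stronger readings are tempting, and the documents do not support them.

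- **That 44 matches cannot be found.** This depends on assumed distributions. Section 9.2 does not say how many race/ethnicity groups or seasons there are. With coarse coding, 44 or more matches before attrition are likely (settings A and B). Only the shortfall from 50 holds in every setting tried.
- **That the allowance is only 6.2% per person** (1 − √0.88). This requires controls to be lost independently after pairing. Sub-study sections 3.0 and 6.0 say the assays use stored main-study samples, and no time is set for choosing controls, so control loss need not cost pairs. Choosing controls among completers does condition them on retention, but a case also needs a week-48 sample to enter the paired test.
- **That power falls to 75%, 69% or 64%** (39, 34 or 31 pairs). Those figures use the SD_d of 46.3%, which is solved backwards from the plan's 80% and is not stated anywhere. If 40% is the SD of the pair difference, 34 pairs still give 81%. If it is per subject with no pair correlation, the full 50 pairs give only 69%, whatever the matching achieves.

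It can also be said that this is an optional pilot sub-study with no bearing on the main trial's primary result, and that covariate-adjusted regression is already planned. Both are true. They limit the weight of the point and make the remedy cheap. What stands is the conflict between the two matching rules, the missing allowance for unmatched cases, the missing fallback and the undefined SD.

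**Conclusion.** The concern holds in a limited form. Section 9.2 and the synopsis give different matching rules. Under the five-factor rule, all 50 pairs are unlikely in every setting examined (probability at most about 0.26, averages about 29 to 49). With an assumed 10% loss of cases only, 44 complete pairs are unlikely in most settings. Section 9.1 provides for attrition but not for unmatched cases.

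These results rest on assumed age, BMI, race and season distributions and on an assumed loss rate, because the documents supply none. No single loss of power can be stated: it runs from negligible to substantial according to what the 40% SD means. Section 9.1 needs that SD defined in any event, because 44 pairs do not follow from 20% and 40% under either plain reading.

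**What to change.** 1. **Section 9.2 and the synopsis:** use one reduced set of matching factors in both, for example age and BMI as in the synopsis, plus arm. Arm splits both sides evenly (about 25 cases and 175 controls per arm), so the 7:1 ratio of controls to cases is kept.
2. **Section 9.2, primary analysis:** use linear regression of the week 24 to 48 change in P1NP on group, with race/ethnicity and season of entry as covariates alongside the matching factors, keeping every case and control with data. This promotes the regression already planned as a sensitivity analysis and leaves the change endpoint as stated.
3. **Section 9.1 and the synopsis:** state the SD of the pair differences, or the within-pair correlation. Then restate the expected number of analysable pairs and the power, with separate allowances for attrition and for unmatched cases.

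The cost is wording and a change in which analysis is primary, with no further subjects or assays. The downsides are somewhat more reliance on a regression model in a non-randomised comparison, and a stated power that may be less favourable.
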